1. **Usual Case Management (UCM) group.** The UCM group will receive the standard Homeless Recovery Program currently offered at The Bridge. In order to qualify for the standard homeless recovery program, individuals must complete The Bridge intake and substantiate homelessness (e.g., provide evidence that they spent the previous night in a shelter or jail). The Bridge intake includes a comprehensive needs assessment, and demographic information is obtained. Following intake, Bridge guests receive a day pass that grants them access to many of the services available at The Bridge (e.g., meals, showers, laundry, phone, mail, library, barber shop, and storage space for their belongings). Those who enroll in The Bridge Homeless Recovery Program receive an identification card and can gain access to additional services including case management, Metro Care (onsite mental health and substance abuse counseling), housing assistance, disability/veteran's benefits assistance, job readiness training, legal aid, and bus passes. Although these services are freely available to all guests enrolled in The Bridge Homeless Recovery Program, many services are offered only during normal business hours and in-person visits are the norm.

Bridge case managers are licensed professional counselors and/or Master's level clinicians who adhere to the **Standard Case Management Model**.^{19,47} Case managers assist homeless adults with: 1) developing care and housing plans; 2) making and maintaining linkages to on- and off-site service providers (e.g., mental health and substance abuse providers); 3) obtaining vital documents needed for housing and income (e.g., birth certificates, state identification, social security cards); 4) job readiness training and placement (if appropriate); 5) overcoming barriers related to criminal history; 6) development of and re-connection with support systems; and 7) transitioning from homelessness to appropriate housing. Case managers also advocate on behalf of homeless adults by serving as a connection between all agencies that will be assisting the guest, their families, and any other involved parties. Guests are encouraged to meet with their case managers weekly; however, Bridge data have indicated that those who enroll in the **Bridge Homeless Recovery Program** complete a total of 1.95 and 3.12 case management sessions in the first 1 and 6 months of enrollment, respectively.

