Visit 2: This visit will take approximately 1 hour to complete. During this visit, participants will be randomized to one of three study conditions. All participants will complete additional study measures. Two-thirds of all participants will receive a smartphone. Those who are randomized to the smartphone groups will be shown how to use the phone to complete assessments, and how to use the app features. Researchers will utilize the participant's Google Play Store account to download the Insight app. Those participants who are randomized to receive smart phones during visit 2 will have an app blocker installed on their phone to prevent phone loss. This app blocker will prevent the participant from access to the phone settings, the Google Play Store or allow deletion the Insight App. Only the research staff will have the password required to access those functions or delete the Insight App. At visits 3 or visit 4, the app blocker will be removed for participants who completed 50% or more of the daily EMA Surveys over the past 30 days as an additional incentive. At the conclusion of the study, the Insight app, and all app data will be removed from the phone, and the phone will be given to the participant to keep. The study data will be removed from the phone and all data collection through the Insight application will end. Researchers will delete the app from the phone and advise the participant the study has concluded. At visit 2, study participants will receive three referral coupons to pass on to others who are interested in the study. If a coupon recipient successfully completes visit 1, the participant who made the referral will be compensated \$20 on the study credit card, for a maximum of 6 successful referrals. Each coupon will include a random unique identification number that identifies the person who provided the coupon and will be valid for the 6 months the participant is active in the study. Participants will be given up to 6 coupons in total if the initial coupons have been distributed. The study team may replace lost or destroyed coupons at their discretion. Participants have a 14-day period to complete visit 2 and be randomized into one of the study conditions. Participants who are not randomized within the 14-day period will be terminated from the study.

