All randomized participants will be included in the analyses and the trial will end once 462 participants are randomized and complete all study components. Preliminary data analyses, manuscript preparation, and conference presentations will begin in Year 2.

Aim 1. The number of participants ($n = 144$ in each group) was estimated based on the following assumptions: 1) random allocation of participants between 3 conditions; 2) type I error rate set to 0.05; 3) a 30% dropout rate for each condition;²³ 4) targeted minimum power of 0.9, and 5) a conservative increase of 4.5 case management sessions between the UCM and SPCM conditions across the 6-month study period. The estimated increase in in case management sessions is based on Lucht et al.,⁴⁹ which showed that 20% of all phone-based prompts to connect with an alcohol treatment counselor resulted in actual treatment sessions. Mondays, the daily EMA items and additional items will be assessed. Additional Monday items will cover topics/variables that have less day-to-day variability (e.g., arrest; witnessing crimes or violence; emergency room visits; hospitalization; quality of life). Examples of EMA constructs that will be assessed are listed in Table 3 and actual EMA items are included in the Appendix.

	Compensation (Usual Care)	Compensation (Smartphone Groups)
Visit 1 (Today)		
Questionnaire	\$30	\$30
Visit 2 (Within 3 Days)	\$30	\$30
Visit 3 (1-Month Follow-Up)		
Questionnaire	\$50	\$50
Phone Assessments	N/A	Up to \$50 every 15 days for survey completion (\$100)
Visit 4 (3-Month Follow-Up)		
Questionnaire	\$50	\$50
Phone Assessments	N/A	Up to \$50 every 15 days for survey completion (\$200).
Visit 5 (6-Month Follow-Up)		
Questionnaire	\$50	\$50
Phone Assessments	N/A	Up to \$50 every 15 days for survey completion (\$300).
TOTAL:	Up to \$210	Up to \$810

Analyses. Primary analyses for this aim will compare counts of the total number of case and crisis management sessions that occurred between the randomization visit and the 6-month follow-up across the 3 conditions using analysis of covariance (ANCOVA). Covariates may include race/ethnicity, age, sex, lifetime months homeless, type of arrest (e.g., violent vs. non-violent), substance abuse or mental health diagnoses,

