and education. The Tukey-Kramer adjustment will be used to examine all pairwise comparisons across conditions. We will also determine if the intervention has similar effects across races, gender, and age**Aim 2**. Based on the available data in criminal justice and homeless populations, we expect a 30% reduction in alcohol and drug use days in SPCM and a 15% reduction in alcohol and drug use days in UCM+SP compared with UCM.^{3,126} Given these expected differences, the proposed sample size of 462 participants (144 per condition) will yield 90% minimum power for comparing the frequency of alcohol and drug use days across conditions. Furthermore, the proposed sample size of 462 participants has 80% minimum power to detect a 24% greater decrease in psychiatric symptoms¹²⁷ in the SPCM group and 10% greater decrease in the UCM+SP group relative to UCM.

Analyses. Multi-level models, also known as mixed models will assess the impact of condition on alcohol and drug use and psychological distress. This method considers the auto correlated nature of this data, and 'unstructured' covariance may be specified to account for the unequal spacing of observations (in-person and EMA data). Covariates for analyses will include baseline characteristics that are known predictors of each outcome, including age, race/ethnicity, employment status, criminal history, and periods of lifetime homelessness. We will also test for interactions between treatment and key demographic variables (e.g., race, ethnicity, gender, and age).

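### Aim 1 counts sessions from a variable point on a front-loaded curve, and the optional covariate list names neither prior sessions nor time since shelter enrollment, so a precision gain is left unsecured

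*Combined protocol and SAP*

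**What the plan says.** Study Conditions, item 1 (UCM), gives the shelter's experience: enrollees "complete a total of 1.95 and 3.12 case management sessions in the first 1 and 6 months of enrollment, respectively".

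Statistics, Aim 1, Analyses, sets the primary comparison. It tallies "case and crisis management sessions that occurred between the randomization visit and the 6-month follow-up across the 3 conditions using analysis of covariance (ANCOVA"). It continues: "Covariates may include race/ethnicity, age, sex, lifetime months homeless, type of arrest (e.g., violent vs. non-violent), substance abuse or mental health diagnoses", and the list ends with education.

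Three other places bear on timing and data:
- **Participant Recruitment:** people enroll in the shelter program first and are then sent to study staff for screening. No interval is given.
- **Study Procedures:** randomization is planned within 72 hours of baseline, but under Visit 2, "Participants have a 14-day period to complete visit 2 and be randomized into one of the study conditions". Visit 5 is dated from Visit 1, not from randomization.
- **Sources of Materials:** three data sources are listed (in-person, EMA and arrest data). Shelter case-management records are not among them.

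**The concern.** Two people in the same arm can start their outcome count at different points on a steeply falling curve. They can also have used different numbers of sessions before the count begins. Both facts are fixed before randomization, and the earlier count measures the same behavior as the outcome. If neither is in the model, whatever variance they predict stays in the error term of a primary analysis. Because Visit 5 is dated from Visit 1, later randomization also shortens the counting window. At stake is the width of the confidence intervals for the three pairwise comparisons, not their validity.

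**Working it through.** **Inputs from the documents.** Usual-care sessions: 1.95 in month 1 and 3.12 in six months. Baseline to randomization: 3 days planned, 14 allowed. Aim 1: 144 per group, 30% dropout, 90% power, alpha 0.05, difference of 4.5 sessions. Not given: an SD, a count distribution, a covariate correlation, or the gap from shelter enrollment to baseline.

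**1. Front-loading.** 1.95/3.12 = 62.5%. Daily rate in month 1: 1.95/30.4 = 0.0641. In months 2-6: (3.12 − 1.95)/152 = 0.0077. The ratio is 8.3.

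**2. Expected sessions lost to delay.** Assume a constant rate within month 1, enrollment on the day of Visit 1, and a count ending six months after Visit 1.
- 3 days: 3 × 0.0641 = 0.19 sessions (6% of 3.12), leaving 2.93.
- 14 days: 14 × 0.0641 = 0.90 sessions (29%), leaving 2.22.

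If the count instead ran a full six months from randomization, 2.95 and 2.33 would remain.

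**3. The plan's sample size.** It cannot be reproduced without an SD. With 144 × 0.70 = 100.8, about 101 completers per arm, 90% power for 4.5 sessions at unadjusted two-sided 0.05 implies SD = 4.5/[(1.96 + 1.2816) × √(2/101)] = 9.87. No covariate gain is assumed in that figure.

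**4. Variance explained in usual care (assumed model).** Let each person's rate be the shelter rate times a gamma multiplier with mean 1 and variance 1/k, with Poisson counts given the rate. For an assumed SD of the six-month count, k = 3.12²/(SD² − 3.12). With expected counts *a* before and *b* after randomization at a fixed gap, prior sessions explain

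R² = (ab/k)² / [(a + a²/k)(b + b²/k)].

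Near-Poisson case, SD 2.2: k = 9.73/(4.84 − 3.12) = 5.66.
- 3 days (a = 0.19, b = 2.93): 0.0099/(0.199 × 4.44) = 1%.
- 14 days (a = 0.90, b = 2.22): 0.124/(1.04 × 3.09) = 4%.

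For gaps that vary between people, I simulated the same model and regressed the later count on prior sessions and days since enrollment together:

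| Assumed SD | Gaps uniform 0-3 days | Gaps uniform 0-14 days |
|---|---|---|
| 3.12 | 4% | 13% |
| 5 | 14% | 33% |

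Prior sessions do most of the work. With gaps of 0-14 days they alone give about 9% of the 13%, and 29% of the 33%. Days since enrollment alone explain under 2% at every SD considered. Their value is in interpreting the prior count: two sessions in three days mean something different from two in fourteen.

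**5. What that is worth.** The equivalent increase in sample size is 1/(1 − R²): 1.01 at 1%, 1.15 at 13% and 1.49 at 33%.

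**6. Chance imbalance in timing.** For gaps uniform over 0-14 days, the SD is 14/√12 = 4.04 days, or 4.04 × 0.0641 = 0.26 sessions. The SE of the between-arm shift is 0.26 × √(2/101) = 0.036, so the 95% range is about ±0.07 sessions, or 0.07/4.5 = 1.6% of the target difference.

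**The case against.** The strongest case against is that nothing in the plan is wrong. Timing and prior use are balanced by randomization in expectation, Type I error is unaffected, and the power statement claims no covariate gain. All of that stands. Several stronger readings are tempting but not supported:

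- **That the plan excludes this adjustment.** The list says covariates may include the named items. It is open, so the gap is one of pre-specification.
- **That a delay typically removes 0.9 sessions.** That is the 14-day limit. At the planned 72 hours the figure is 0.19. Both run from baseline, and the earlier gap from shelter enrollment is unknown.
- **That chance imbalance in timing threatens the comparison.** At gaps of 0-14 days it does not (step 6).
- **That a definite gain can be claimed.** A prior-to-later correlation of 0.3-0.5 would cut variance by 9-25%, but no document supports that range. Using SD 9.87 in the same model gives 39% to 55%, but that SD is back-solved from the planned effect and is not a usual-care figure.

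Two further limits stand. The shelter figures describe program enrollees under usual care. In SPCM, prompts may change who uses services, which could weaken the link with prior use. There, 0.90 would be only about 12% of the expected 3.12 + 4.5 = 7.62 sessions. The outcome also includes crisis sessions, for which no time pattern is given.

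**Conclusion.** The point holds as a precision issue. The documents establish the front-loaded use, the count that starts at randomization, the variable interval before it, and the absence of both variables from the named covariates. They do not establish the size of the loss. In usual care, with randomization within 14 days of shelter enrollment, the gain from both covariates runs from about 1% of outcome variance (near-Poisson counts, gaps of about 3 days) to about a third (SD 5, gaps spread over 0-14 days). It rests on the gamma-Poisson model, a constant rate within month 1, and assumed SDs and gaps. The range is not a ceiling, because a larger SD or longer gaps would raise it. The change is still worth making: the possible benefit runs from negligible to substantial, and adjusting for pre-randomization variables carries no post-treatment bias.

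**What to change.** In Statistics, Aim 1, Analyses, name two fixed covariates:
1. the number of Bridge case-management sessions completed before randomization;
2. the number of days from Bridge enrollment to randomization.

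State that both are in the primary model whatever the data show. If only one can be obtained, prior sessions matter more.

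Add to Sources of Materials the record from which session counts are taken, and draw both covariates from it. The outcome needs that source named in any case.

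The cost is two degrees of freedom out of several hundred, two extra data fields and a few lines of text. That the fields are easy to obtain is an assumption until the sponsor identifies the record.

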(e.g., assessing the number of drinks consumed or level of depression or anxiety over the past week or month).^{42,43} Ecological momentary assessment (EMA), in which handheld devices are used to capture “real time” experiences that vary daily (or from moment to moment), is currently the most accurate way to measure phenomena in real time in natural settings.^{42,44} Although EMA has been used in a variety of populations and with multiple health outcomes, only one study⁴⁵ outside of our own work⁴⁶ has collected EMA data in homeless adults. The proposed study will identify key variables, measured proximally (EMA data) and distally (traditional in-person assessments and EMAs), that predict re-arrest and homelessness. These rich data will address knowledge gaps that have limited our understanding of and ability to intervene in this marginalized population.

Overall, the significance of this trial will be to evaluate a technology-driven application to increase access to service providers in a highly vulnerable group of homeless adults and to thereby decrease the likelihood of re-arrest and homelessness. In addition, we hope to improve our understanding of the proximal and distal factors that contribute to homelessness and incarceration recidivism. This contribution is significant because it is a step towards the development of practical, inexpensive, and effective interventions for homeless adults.

Objectives:

Our long-term goal is to reduce health disparities among recently incarcerated homeless adults.

The primary study objectives will be attained by pursuing the following specific aims:

- a. **To compare case management and crisis management service utilization among recently incarcerated homeless adults who are randomized to the UCM, UCM+SP, and SPCM conditions.** It is hypothesized that homeless adults assigned to SPCM will utilize more case management and crisis management services than those assigned to UCM or UCM+SP.
- b. **To compare the effect of treatment condition on alcohol use, drug use, and psychological distress.** It is hypothesized that the SPCM group will demonstrate greater improvements in each outcome compared to UCM+SP or UCM

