1. **In-person data.** Demographic, psychosocial, environmental, and behavioral data will be collected from all participants via traditional self-report questionnaires during 5 in-person visits (i.e., baseline visit, the randomization visit [within 72 hours of the baseline visit], the 1, 3- and 6-month follow-up visits) on a laptop or tablet computer using Questionnaire Development System (QDS) software (see detailed description below). If in-person visits are not possible, interviews will be conducted over the telephone and manually entered into the QDS system by Link2Care staff. In addition, participants will complete timeline follow-back measures with study researchers to determine homeless nights, alcohol use, and other substance use. These in person visits will occur at The Bridge Homeless Shelter or at another location in the community if the participant is unable to attend their appointment at The Bridge. Additionally, these in-person visits may be conducted over the phone when in-person visits are not possible, or by texting or e-mailing a link to the REDCap survey. Information regarding residency status, social security number and if participants are employees of The University of Oklahoma Health Sciences Center (OUHSC), will be collected at baseline visit using a questionnaire. This information will not be utilized in data analysis and is being collected for Federal Tax purposes as required by The University of Oklahoma Health Sciences Center. If participants earn \$600 or more, OUHSC will report the income to the IRS and mail a form 1099 to the participant’s address by January 31 of the following year.

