3. **Arrest data.** The Dallas County Jail collects and maintains a dataset that contains demographic characteristics (including homelessness status), and arrest data on all individuals who are arrested in the County. [name] will have access to this dataset for the purposes of this study (see **Director of Criminal Justice Letter of Support**). Specifically, [name] will receive a complete updated and encrypted dataset of all arrested study participants from a Dallas County employee every 6 months. Upon receipt, she will search the dataset for study participants and record whether a participant was arrested or not, the date(s) of arrest, and the class and type of the alleged crime (e.g., violent vs. non-violent, property crime, misdemeanor, felony) in a new study dataset. This arrest data will be used as one of the primary outcome variables for this study. Dallas City Jail records are publicly available online at <https://www.municipalrecordsearch.com/dallastx/Cases>. This database will augment County Jail records and be searched to determine eligibility and arrest.

Study Population:

Consistent with our previous research with this population, we have limited exclusion criteria so that the sample is as broad and representative of the population as possible. Interested individuals (N=462 will be included in the study if they: 1) were released from Dallas County Jail in the past 60 days; 2) plan to reside in the Dallas area for the next year, 3) enroll in The Bridge Homeless Recovery Program, 4) are willing and able to attend the visit, randomization visit, and the 1, 3, and 6-month follow-up visits; 5) score ≥ 4 on the REALM- SF indicating > 6 th grade English literacy level (i.e., a 7th grade reading level is necessary to complete assessments; 12% to 14% of those screened for Projects Advance and Aspire had REALM scores < 7 th gradereading level; < 1 % of Bridge guests are non-English speakers), 6) read aloud from the Informed Consent document to ensure understanding, and 7) score > 24 on the Mini-Mental State Exam indicating no substantialcognitive impairment.

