Participants have reported few problems using the QDS program, including those with no computer experience. Staff will be available to help participants who may have difficulty. The amount of time needed to complete the QDS administered questionnaires varies by study visit. Based on our previous experience with collecting data in homeless adults we estimate that the baseline visit will require approximately 1-2 hours to complete and follow-up assessment visits will require approximately 1-2 hours. Note that although breaks have been encouraged in our previous studies that have used QDS assessments in this homeless population, none actually took breaks. Examples of traditional measures are listed in Table 2 and include multiple constructs that are hypothesized to directly and indirectly (i.e., mediation of the treatment effect) affect the study outcomes. In addition, barriers to phone-based case management sessions and staff and participant perceptions of the SPCM app will be assessed.

See Appendix A for measure descriptions, assessment items, and a schedule that indicates which measures will be administered at each visit. In addition to the QDS System, assessment data may be collected through the REDCap system. REDCap is a secure web application for building and managing online surveys and databases and is specifically tailored for the management and administration of online data collection for research studies.

Alcohol/drug use, re-arrest, and number of homeless nights will be collected using a Timeline Follow-back procedure (See Appendix) at all 1, 3, and 6-month follow-up visits. In addition, arrest data from the Dallas County Jail and the Dallas City Jail will be examined to identify participants who are re-arrested within 12- months of the randomization visit (see **Director of Criminal Justice Letter of Support**). This will provide an objective measure of the date and time of arrest as well as a description of the offenses that occurred. The research team will share participant's name and date of birth to obtain this information, but no additional information that the participant provides to us over the course of the study will be shared with this Dallas County employee or the Jail. For participants who complete online surveys via REDCap, the participant will be instructed to call the research team to complete the Time Line Follow Back for location, drug and alcohol use.

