Approval for this study is being sought from the Committee for the Protection of Human Subjects (CPHS) of the University of Texas Health Science Center at Houston. Individuals who were released from the Dallas County Jail or the Dallas City Jail in the past month and present at The Bridge will complete a shelter intake form, be given a Bridge identification badge, and enroll in the Bridge Homeless Recovery program if interested (this is the current standard of care at The Bridge). These individuals will receive information about this completely voluntary study and will be informed that Bridge services are not contingent upon study enrollment. Eligible adults who remain interested the study will be directed by The Bridge Triage/Intake Coordinator (see Bridge Subcontract) to the study research staff for screening. Informed consent will be obtained prior to screening for this study.

Data handling and record keeping:

General Procedures. Each participant will be assigned an identification number that will be utilized in place of names in all electronic and print data files. The sheet containing the links between participant names and identifiers will be kept in locked filing cabinet when not in use and will be destroyed 12 months after data collection has been completed. All print information, including informed consent and screening questionnaires, will be stored in a separate locked filing cabinet in [name] office. All electronic data (with names omitted) will be maintained on the investigator’s computers, and all computers and electronic files will be password protected. Because sensitive data will be collected, a Certificate of Confidentiality has been obtained to ensure that data cannot be subpoenaed and used against participants in court, and this information will be explained to all participants during the informed consent process.

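### Aim 2 should adjust for each outcome's Visit 1 value and for days since jail release, and estimate the between-arm difference at follow-up, because custody may lower a post-release baseline

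*Combined protocol and SAP*

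**What the plan says.** **Entry.** Study Population, criterion 1, admits people who "were released from Dallas County Jail in the past 60 days". Participant Recruitment repeats 60 days and adds the City Jail. The Ethics section instead describes people "released from the Dallas County Jail or the Dallas City Jail in the past month and present at The Bridge". Under Study Conditions, a previous night in jail is accepted as evidence of homelessness, so Visit 1 can follow custody almost directly.

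**Measurement.** Sources of Materials, 1 (In-person data), in the paragraph that covers all five visits, says "participants will complete timeline follow-back measures with study researchers to determine homeless nights, alcohol use, and other substance use". Study Procedures sends the reader to Table 2 for the Visit 1 measures, and Table 2 lists the alcohol and drug follow-back. Traditional Measures (in-person), however, says that these outcomes "will be collected using a Timeline Follow-back procedure (See Appendix) at all 1, 3, and 6-month follow-up visits", with no mention of baseline. No look-back length or rule for custody days appears in the supplied text; the Appendix is not part of it. The phone assessments cannot supply a baseline, because only the two smartphone arms receive them and they begin the day after randomization.

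**Analysis.** Objective b hypothesizes that "the SPCM group will demonstrate greater improvements in each outcome compared to UCM+SP or UCM". Aim 2 uses mixed models for alcohol and drug use and for psychological distress, with covariates that are baseline predictors of each outcome, "including age, race/ethnicity, employment status, criminal history, and periods of lifetime homelessness". Neither the baseline value of the outcome nor time since release is named, and the text does not say how a baseline measurement would enter the model.

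**The concern.** Opportunities to drink or use drugs are restricted in jail. If the Visit 1 look-back reaches into custody, the baseline count partly reflects how recently the person was released and how long the stay was. A heavy user released the day before can look like a non-user, and will then appear to worsen in any arm. If the follow-back is done only at follow-up, there is no pre-randomization value of the substance-use outcomes at all.

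Either way, two things are at stake. Improvement within an arm cannot be read at face value. And the analysis may lose precision, either by leaving out a useful prognostic variable or by subtracting a noisy one.

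**Working it through.** **1. The plan's own figure.** Aim 2 states 90% minimum power for a 30% reduction in use days (SPCM) and a 15% reduction (UCM+SP) against UCM, with 144 per condition. No mean, SD or between-visit correlation is given, so this cannot be rebuilt. What can be found is the spread it implies. Inputs are the 30% dropout from Aim 1, so 144 × 0.7 = 100.8 completers per arm, and alpha 0.05, taken as two-sided (an assumption).

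- Standardized difference for 90% power: (1.960 + 1.282) × √(2/100.8) = 0.457.
- Largest SD/mean ratio for a 30% reduction: 0.30/0.457 = 0.66. For a 15% reduction: 0.15/0.457 = 0.33.

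The stated 90% is neither confirmed nor refuted. It serves below as the benchmark for a follow-up-only comparison. (Separately, 3 × 144 = 432, not 462. The relative comparison in step 5 does not depend on this.)

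**2. Custody days in a Visit 1 look-back.** Let t be days from release to Visit 1, W the look-back and L the jail stay. Custody days in the window are min(L, max(0, W − t)). Assume t uniform on 0 to 60 and W = 30.

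- Share affected: 30/60 = 50%.
- L of 30 days or more: mean (30²/2)/60 = 450/60 = 7.5 days (25% of the window).
- L = 7: mean (23 × 7 + 24.5)/60 = 185.5/60 = 3.1 days (10%).

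The answer depends on the unstated window. A 7-day look-back reaches custody for 7/60 = 12% of participants; a 60- or 90-day look-back does so for all. If entry is within 30 days, as the Ethics section implies, a 30-day look-back reaches custody for all, averaging 185.5/30 = 6.2 days (7-day stays) to 450/30 = 15 days (stays of 30 days or more).

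**3. Within-arm change.** A simulation used 3,000 runs, 101 per arm, average use on 30% of days at liberty, a stable propensity per person, W = 30, long stays and t uniform on 0 to 60. In a control arm with no true change, mean use days rose from 6.7 at baseline to 9.0 at follow-up. By hand, 0.30 × (30 − 7.5) = 6.75 against 0.30 × 30 = 9.0. That is an apparent worsening of 9.0/6.7 − 1 = 34%, larger than the planned 30% effect.

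**4. Between-arm difference.** With a true 30% reduction (0.30 × 9.0 = 2.70 fewer days), the estimates were −2.69 (follow-up only), −2.69 (baseline-adjusted) and −2.70 (change score). Under no effect, rejection rates were 4.5% to 5.7%. Custody does not bias the arm contrast.

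**5. Precision.** Relative to follow-up only (variance factor 1), a change score has factor 2(1 − ρ) and baseline adjustment 1 − ρ², where ρ is the baseline to follow-up correlation. With the benchmark at 90%, power = Φ(3.242/√factor − 1.960).

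| ρ (assumed) | Follow-up only | Change score | Baseline-adjusted |
|---|---|---|---|
| 0.2 | 90% | 72.7% | 91.1% |
| 0.3 | 90% | 78.2% | 92.5% |
| 0.5 | 90% | 90.0% | 96.3% |
| 0.7 | 90% | 98.7% | 99.5% |

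Because 1 − ρ² = (1 − ρ)(1 + ρ), for ρ between 0 and 1 it never exceeds 1 or 2(1 − ρ). Adjustment is therefore never the less precise choice, while a change score loses to follow-up only whenever ρ is below 0.5. Custody days would be expected to lower ρ. The simulation, which holds each person's propensity fixed and so has a high ρ, shows the favourable end: power was 76.7% follow-up only, 97.5% change score and 98.7% adjusted.

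**The case against.** Several points on the other side stand.

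- **The comparison is between concurrent randomized arms.** Objective b and the Aim 2 power statement both compare with UCM. A reader might infer that Aim 2 lacks any valid reference; it does not, and step 4 shows no bias.
- **The look-back is not stated.** The Appendix may settle whether a Visit 1 follow-back exists, its window and its coding of jail days. The follow-back also records location, so custody days may already be identifiable. That a baseline would reach into custody is therefore plausible, not established.
- **The covariate list is open-ended.** A baseline outcome would fit it, and a mixed model can carry baseline as a repeated measure. It is correct to say these variables are not named; it is not correct to say they are excluded. Still, leaving them open defers the choice of an important covariate. An unconstrained arm-by-visit contrast is in essence the change-score comparison of step 5.
- **The reach is limited.** Homeless nights might seem to be affected too, but they are analysed in Aim 3 from follow-up visits. Psychological distress is not a follow-back measure, so the custody argument does not touch it. For distress only the general case for baseline adjustment applies.
- **The gain may be small.** At ρ = 0.2, adjustment moves 90% only to 91.1%. The larger loss arises only if change is analysed, and Aim 2 does not expressly plan that.

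**Conclusion.** The point holds as a prespecification gap, worth fixing because the remedy is nearly free. A Visit 1 follow-back may include custody days for about half of participants, averaging about 3 to 7.5 of 30 days, under an assumed 30-day window and release uniform over 0 to 60 days. Other windows give anything from 12% to all participants affected. The arm contrast is unbiased however baseline is handled. What suffers is the reading of within-arm improvement (a spurious 34% worsening in the long-stay simulation) and, depending on the analysis, precision: about 73% power for a change score against 91% with adjustment, at an assumed ρ of 0.2 and a 90% follow-up-only benchmark. The documents give no release-to-baseline times, jail stays or correlations, so these figures are illustrations and not estimates for this trial.

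**What to change.** - **Statistics, Aim 2, Analyses:** name as fixed covariates the Visit 1 value of each Aim 2 outcome and the days from jail release to Visit 1. Define the treatment effect as the adjusted between-arm difference at follow-up, not change from baseline. If Visit 1 is kept as a repeated measure in the mixed model, constrain the baseline means to be equal across arms.
- **Schedule:** reconcile In-person data, Visit 1 with Table 2, and Traditional Measures so that the alcohol and drug follow-back is done at Visit 1, before randomization, with its look-back stated.
- **Custody days:** record them in the look-back, and either express use per day at liberty or keep the custody count alongside the use count. State what is done when few or no days at liberty fall in the window, since a rate based on one day is very noisy.
- **Entry criteria:** reconcile the 60-day and past-month statements, and County Jail only with County or City Jail.
- **Optional:** anchor the look-back to a period in the community before the index arrest. This avoids custody days but lengthens recall across the jail stay plus up to 60 days, so it is a trade-off and not a requirement.

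The cost is two covariates and a small amount of extra recording at Visit 1. Entry already requires evidence of recent release, so for participants already enrolled days since release should be recoverable wherever the release date was kept.
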